## Group C:

• Change from Baseline to Week 24/EOT in the mean dysmenorrhea NRS score;

Effective: 12-MAR-2018

- Change from Baseline to Week 24/EOT in the mean NMPP NRS score;
- Change from Baseline to Week 24/EOT in the severity scores on the PGA for dysmenorrhea;
- Proportion of patients who are better or much better on the PGIC for dysmenorrhea at Week 24/EOT;
- Change from Baseline to Week 24/EOT in the severity scores on the PGA for NMPP;
- Proportion of patients who are better or much better on the PGIC for NMPP at Week 24/EOT.
- Change from Baseline to Week 24/EOT in the mean dyspareunia NRS scores.
- Proportion of patients who are better or much better on the PGIC for dyspareunia at Week 24/EOT;
- Change from Baseline to Week 24/EOT in the mean dyspareunia functional impairment on the sB&B scale;
- Change from Baseline to Week 24/EOT in severity scores on the PGA for pain;
- Proportion of responders at Week 24/EOT based on their EHP-30 Pain Domain score;
- Change from Baseline to Week 24/EOT in function impairment on the PGA for function;
- Change from Baseline to Week 24/EOT in each of the non-pain EHP-30 domains (Control and Powerlessness, Social Support, Emotional Well-Being, and Self-Image);
- Change from Baseline to Week 24/EOT in the mean dysmenorrhea functional impairment on the sB&B scale;
- Change from Baseline to Week 24/EOT in the mean NMPP functional impairment on the sB&B scale.

The following secondary endpoints will be assessed comparing Group B with Group C:

- Proportion of responders at the Week 24/EOT pain assessment period, based on their dysmenorrhea NRS scores recorded in a daily eDiary;
- Proportion of responders at the Week 24/EOT pain assessment period, based on their NMPP NRS scores recorded in a daily eDiary.
- Change from Baseline at Week 24/EOT in the EHP-30 Pain Domain scores.
- Proportion of responders at Week 24/EOT based on their EHP-30 Pain Domain score.

Dyspareunia analyses will be performed only in patients who had vaginal sexual intercourse during both the Baseline pain-assessment period and Randomized Treatment Periods.

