#### 9.3. Efficacy Analyses

Unless otherwise specified, efficacy analyses will be conducted using the mITT Population according to the randomized treatment assignment, and stratified analyses will be stratified by the randomization stratification factors. If the group of patients from any of the individual randomization stratification factors (eg, patients with a time from diagnosis of endometriosis < 5 years) comprises less than 10% of the entire mITT population, this stratification factor will be ignored for stratified analyses.

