### 9.3.2. Secondary Efficacy Endpoints

• Change from Baseline at Week 24/EOT in the EHP-30 Pain Domain scores in the relugolix 40 mg group co-administered with low-dose hormonal add-back therapy for 24 weeks versus placebo;

The change at Week 24/EOT from Baseline in EHP-30 Pain Domain comparing Group A and Group C is a key secondary endpoint to which Type 1 error protection will be extended.

Effective: 12-MAR-2018

To assist in score interpretation, a meaningful within-patient score change threshold for the EHP-30 pain domain will be determined using a similar approach as that for the primary endpoint. A responder at Week 24/EOT based on EHP-30 pain domain scores is defined as a patient who had a reduction of the determined threshold or greater from Baseline using PGA for function as the anchor. Proportion of responders at Week 24/EOT based on EHP-30 Pain Domain scores is a secondary endpoint;

The following secondary endpoints will be assessed comparing Group A with Group C. The Statistical Analysis Plan will specify to which additional secondary endpoints Type 1 error protection will be extended.

- Change from Baseline to Week 24/EOT in the mean dysmenorrhea NRS score;
- Change from Baseline to Week 24/EOT in the mean NMPP NRS score;
- Change from Baseline to Week 24/EOT in the severity scores on the PGA for dysmenorrhea
- Proportion of patients who are better or much better on the PGIC for dysmenorrhea at Week 24/EOT:
- Change from Baseline to Week 24/EOT in the severity scores on the PGA for NMPP.
- Proportion of patients who are better or much better on the PGIC for NMPP at Week 24/EOT;
- Change from Baseline to Week 24/EOT in the mean dyspareunia NRS scores.
- Proportion of patients who are better or much better on the PGIC for dyspareunia at Week 24/EOT;
- Change from Baseline to Week 24/EOT in the mean dyspareunia functional impairment on the sB&B scale:
- Change from Baseline to Week 24/EOT in severity scores on the PGA for pain;
- Proportion of responders at Week 24/EOT based on EHP-30 Pain Domain scores;
- Change from Baseline to Week 24/EOT in function impairment on the PGA for function;
- Change from Baseline to Week 24/EOT in each of the non-pain EHP-30 domains (Control and Powerlessness, Social Support, Emotional Well-Being, and Self-Image);
- Change from Baseline to Week 24/EOT in the mean dysmenorrhea functional impairment on the sB&B scale;

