#### 9.3.2.1. Secondary Efficacy Endpoint Analyses

If the treatment effects for both co-primary endpoints are statistically significant each at 2-sided 0.05 alpha level, the key secondary endpoint of change from Baseline at Week 24 in the EHP-30 Pain Domain scores will be tested comparing the relugolix Group A versus placebo Group C at a 2-sided 0.05 alpha level. The comparison will be performed using a mixed model repeated measures approach with treatment, randomization stratification factors, and treatment by visit interaction included as fixed effects and baseline value included as a covariate and an unstructured covariance. The dependent variable (change from Baseline) for each patient at each visit will be calculated based on the visit windows specified in the Statistical Analysis Plan. Based on this model, the difference in least squares means of change from Baseline between the two groups and corresponding 95% CI and p-value will be presented at Week 24 comparing Group A with Group C.

If this key secondary endpoint is positive, additional secondary efficacy endpoints to which Type 1 error protection will be extended will be tested comparing Group A with Group C using a closed testing procedure to control the familywise error rate at a 2-sided alpha level of 0.05. The details of the closed testing procedure will be provided in the Statistical Analysis Plan, which will be finalized prior to unblinding the trial.

For endpoints evaluating the change from Baseline to Week 24/EOT, treatment comparisons will be performed using a mixed model repeated measures approach with treatment, randomization stratification factors, and treatment by visit interaction included as fixed effects and Baseline value included as a covariate. The dependent variable (change from Baseline) for each patient at each visit will be calculated based on visit windows specified in the final Statistical Analysis Plan. In addition, descriptive statistics will be provided by treatment group and by visit.

For endpoints evaluating proportions, treatment comparisons will be performed using a stratified Cochran-Mantel-Haenszel test.

The daily average sB&B scores for each patient during a specific pain assessment period will be on a continuous scale for the secondary endpoints involving sB&B items with the categories as follows: none = 0, mild = 1, moderate = 2, severe = 3.

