Dyspareunia analyses will be performed only in patients who had vaginal sexual intercourse during both the Baseline pain assessment and Randomized Treatment Periods.

The comparison of Group B versus Group C with respect to the responder rates for dysmenorrhea and NMPP as well as the change from Baseline at Week 24/EOT in the EHP-30 Pain Domain scores will be performed in a similar fashion to that for the co-primary efficacy analyses comparing Group A versus Group C described above.

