#### 1 Common

Message 1

Note: Time will populate per device

[figure not shown]
Page 3 of 24

Version 3 US English Screen Report

Please answer the required

Info

question(s)

MY80005-eDiary 23May2017

Message 2

Screen 6

Message 3

Note: Medication Name and Date will show per device

Select the number of pills of 'Ibuprofen 200 mg ' you took today (22-Mar-2017) at 12:00 AM.

If your medication was something other than a pill please indicate the number taken.

Message 4

Screen 7

Next

[figure not shown]
Message 5

Note: Medication Name and Date and time will show per device

Back

Page 4 of 24

Version 3 US English Screen Report

[figure not shown]

MY80005-eDiary 23May2017

Message 6 Screen 8 Screen 9

Note: 'Medication', 'Reason', 'Date and Time', 'Taken' will show per patient selection

Screen 10

Page 5 of 24

Page 6 of 24

Message 8

Screen 13

Message 9

Effective: 12-MAR-2018

Version 3 US English Screen Report

Do you take the medication via the **mouth** for example by swallowing tablets, capsules or drops?

Add New Pain Medication

O Yes

O No

Back

Next

[figure not shown]
MY80005-eDiary 23May2017

Screen 14 Screen 15 Screen 16

[figure not shown]
Next

Back

Screen 17

Page 7 of 24

Page 8 of 24

Version 3 MY80005-eDiary 23May2017 US English Screen Report How would you describe the amount of bleeding in the past 24 hours? For the following question, please select one number to rate your pelvic pain during vaginal sexual intercourse. In the past 24 hours, did you have vaginal sexual intercourse? (For this study, we define vaginal sexual intercourse as penetration of any duration). Spotting Yes Light No Moderate Heavy Extremely Heavy Back Next Back Next > Back Next > Screen 6 Screen 7 Screen 8 How would you rate your worst pelvic pain during vaginal sexual intercourse in the past 24 hours? In the past 24 hours, have you avoided Did you take any medications to relieve vaginal sexual intercourse because you expected it to be painful? any kind of pain over the last 24 hours? 0 1 2 3 4 5 6 7 8 9 10 Screen 9 Yes Back Next Screen 10 Screen 11

Page 9 of 24

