Version 3 MY80005-eDiary 23May2017 US English Screen Report aily Diary For each of the following three Dysmenorrhea (menstrual pain) Pelvic pain symptoms, please select the response that best describes your experience over the past 24 hours. Severe. In bed all day, incapacitation Severe. Requires strong analgesics Moderate. In bed part of day, some loss of work efficiency Moderate. Noticeable pelvic pain Mild. Some loss of work efficiency. Mild. Occasional pelvic pain No pain. No pain associated with No pain. No pelvic pain during past 24 menstruation during past 24 hours. Did not menstruate during the past 24 Back Next > Back Next Back Next > Screen 12 Screen 13 Screen 14 inical Study Medication 11:59 AM inical Study Medication 11:59 AM Daily Diary Deep dyspareunia (pain during intercourse) Did you take your dose of study If yes, please provide: treatment (tablet) today? Time: Severe. Avoids intercourse because of pain Moderate. Intercourse painful to the Yes point of causing interruption 11:59 PM Mild. Tolerated pain No pain. No pain during intercourse No intercourse. No intercourse for other reasons Back Next Back Next Next Screen 15 Screen 16 Screen 17

Page 10 of 24

Page 11 of 24

Screen 21

Back

Back

Screen 20

Save

Screen 22

Effective: 12-MAR-2018

Version 3 US English Screen Report

[figure not shown]
Message 1

MY80005-eDiary 23May2017

Version 3 US English Screen Report

MY80005-eDiary 23May2017

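### The sB&B dyspareunia endpoint drops women with no intercourse on treatment, although avoiding intercourse because of pain is that item's worst scored category

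*Protocol*

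**What the plan says.** Section 9.3.2.1 limits the analysis set for every dyspareunia endpoint: "Dyspareunia analyses will be performed only in patients who had vaginal sexual intercourse during both the Baseline pain assessment and Randomized Treatment Periods". The synopsis repeats the rule after its list of secondary endpoints: "Dyspareunia analyses will be performed only in patients who had vaginal sexual intercourse during both the Baseline pain-assessment period and Randomized Treatment Periods". Neither place exempts any instrument.

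Three Group A versus Group C secondary endpoints fall under the rule: the dyspareunia NRS, the PGIC for dyspareunia, and "Change from Baseline to Week 24/EOT in the mean dyspareunia functional impairment on the sB&B scale" (Section 9.3.2). For the last of these, Section 9.3.2.1 averages the daily item on the coding "none = 0, mild = 1, moderate = 2, severe = 3".

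The item itself is in Appendix 2 (Daily eDiary). Its worst response is "Severe. Avoids intercourse because of pain". A separate response covers absence for any other cause: "No intercourse. No intercourse for other reasons". The diary also asks whether, in the past 24 hours, the patient avoided "vaginal sexual intercourse because you expected it to be painful".

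The default in Section 9.3 is that, unless otherwise specified, "efficacy analyses will be conducted using the mITT Population according to the randomized treatment assignment".

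**The concern.** The restriction suits an instrument that can only be answered after intercourse. The sB&B item is different, because a woman can reach its worst level precisely by not having intercourse. The rule therefore uses absence of intercourse both as the top score and as a ground for removal.

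The condition is also set after randomization. A treatment intended to reduce dyspareunia can change whether a woman has intercourse or avoids it because of pain, so the women retained in the two arms need not be comparable. Any treatment effect on complete pain-related avoidance cannot be seen in an endpoint that is meant to measure functional impairment.

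**Working it through.** **Setting the rules side by side.** Consider a woman with intercourse during the Baseline period.

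| On-treatment behaviour | sB&B scores | In the analysis as written? |
|---|---|---|
| Intercourse at least once in the treatment period, later avoidance because of pain | Observed, avoidance days = 3 | Yes |
| No intercourse, pain as the reason on every scored day | Observed, mean = 3.0 | No |
| No intercourse, other reasons throughout | No numeric code in Section 9.3.2.1 | No |

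The conflict is the second row: her outcome is fully observed and lies at the worst value, yet she is excluded. The first row bounds the problem. The rule refers to the whole Randomized Treatment Period, while the outcome window is the last 35 days (Section 9.3.1), so a single episode at any time on treatment keeps a woman in.

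**Is there a figure to reproduce?** No. The protocol gives no sample size, effect size or avoidance rate for any dyspareunia endpoint, so what follows is an illustration in which every input is assumed.

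**Inputs (all assumed; women with Baseline intercourse only).** Mean change among women with on-treatment intercourse: -0.8 in Group A and -0.4 on placebo. Share avoiding throughout because of pain: *a* in Group A, *p* on placebo. Avoiders end at 3, so their change is *c* = 3 - (their baseline mean).

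**Formulas.**

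- As written: -0.8 - (-0.4) = -0.40, whatever *a* and *p* are.
- Avoiders kept: [(1 - a)(-0.8) + a·c] - [(1 - p)(-0.4) + p·c] = -0.4 + (0.8 + c)a - (0.4 + c)p.
- Baseline 2.0 (c = 1.0): -0.4 + 1.8a - 1.4p.
- Baseline 2.5 (c = 0.5): -0.4 + 1.3a - 0.9p.
- Baseline 2.8 (c = 0.2): -0.4 + 1.0a - 0.6p.

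Worked example, 10% versus 20% at baseline 2.0: -0.4 + 0.18 - 0.28 = -0.50.

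**Effect with avoiders kept (as written: -0.40 throughout).**

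| Avoidance, A vs placebo | Baseline 2.0 | Baseline 2.5 | Baseline 2.8 |
|---|---|---|---|
| 2% vs 4% | -0.42 | -0.41 | -0.40 |
| 5% vs 10% | -0.45 | -0.43 | -0.41 |
| 10% vs 20% | -0.50 | -0.45 | -0.42 |
| 5% vs 5% | -0.38 | -0.38 | -0.38 |
| 4% vs 2% | -0.36 | -0.37 | -0.37 |

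In the first three rows the written rule understates the effect, by between 1% (2% vs 4%, baseline 2.8) and 20% (10% vs 20%, baseline 2.0: 1 - 0.40/0.50). In the last two it overstates it, by 5% (0.40/0.38) to 12% (0.40/0.356 at baseline 2.0).

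The sign of the bias turns where p/a = (0.8 + c)/(0.4 + c): 1.29, 1.44 and 1.67 for the three baselines. Equal avoidance does not remove the bias: with a = p = r the effect is -0.4(1 - r) for any c.

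**Does baseline adjustment change this?** Section 9.3.2.1 specifies a model with baseline as covariate. A simulated baseline-adjusted regression (2 million per arm, baseline mean 2.0, SD 0.4, clipped to 0 to 3) gave -0.396 as written. With avoiders kept it gave -0.416 (2% vs 4%), -0.446 (5% vs 10%), -0.496 (10% vs 20%) and -0.376 (5% vs 5%), close to the closed form. This checks the baseline 2.0 column only.

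**A second set of assumptions.** Using end-of-treatment means of 1.0 (A) and 1.5 (placebo) among retained women, the restricted difference is -0.50. Keeping avoiders at 3 gives, for example, (0.95 × 1.0 + 0.05 × 3) - (0.80 × 1.5 + 0.20 × 3) = 1.10 - 1.80 = -0.70 at 5% vs 20%, and (0.90 × 1.0 + 0.10 × 3) - (0.95 × 1.5 + 0.05 × 3) = 1.20 - 1.575 = -0.375 at 10% vs 5%. Again the bias can go either way.

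**The case against.** The strongest reply is that the rule is a deliberate, prespecified choice. It is worded almost identically in two places, Section 9.3 allows departures from the default population, and it gives one common set for all three dyspareunia instruments. That explains the rule, and for the NRS, which rates pain during intercourse, and the PGIC, which has a not-applicable response, the restriction is natural. It does not rescue the sB&B item, which already distinguishes pain-related avoidance from other absence and scores the former.

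The reach is narrow: only women with Baseline intercourse, none in the whole treatment period, and pain as the reason are wrongly lost. Harm is not demonstrated: all inputs above are assumed, the shift in the main table is at most 0.10 points, and that largest case makes the written rule conservative. Both points stand, and they limit the weight of the concern without removing it.

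The repair is also imperfect. A newly admitted woman with no intercourse can only score 3.0 or be missing, and a mean of 3.0 may rest on few avoidance days. That is true, but the existing scoring already allows it for retained women who have no intercourse in the last 35 days. Women avoiding for pain at Baseline stay excluded; that limits generalizability, but the condition precedes randomization and does not break it.

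Finally, the matter might be thought to belong in the SAP, which was not available here. The protocol, however, fixes this rule itself and does not defer it.

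**Conclusion.** The concern holds. As written, the protocol removes women whose observed sB&B dyspareunia score is the worst possible, on a post-randomization condition that treatment can affect. The resulting comparison is not between the randomized groups.

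Size and direction are unknown, because the protocol gives no avoidance rates or sB&B means. Under the main set of assumptions an as-written -0.40 corresponds to between -0.36 and -0.50, and several cases move it by only a few percent. The conclusion does not rest on those figures; it follows from the analysis-set rule and the item's response categories.

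One secondary endpoint is affected. The co-primary endpoints and the EHP-30 Pain Domain key secondary endpoint are not. This should be corrected, but it does not threaten the trial's main conclusions.

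**What to change.** In Section 9.3.2.1 and in the matching synopsis sentence, add an exception for the sB&B dyspareunia endpoint:

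- Remove the on-treatment intercourse condition and keep the Baseline one, so that the set is fixed before randomization.
- State that days of avoidance because of pain count as 3, and that days without intercourse for other reasons are not scored.
- Keep the current both-periods subset as a supportive analysis.
- Leave the NRS and PGIC restriction as it is.

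The change should be made before unblinding. It costs wording in two places and some programming; the eDiary already records the needed responses daily. There are two drawbacks. The sB&B set may differ from the NRS and PGIC sets and must be labelled as such. Women reporting only other reasons in a window will have missing scores for the mixed model to handle, so some post-randomization selection remains in the form of missing data.

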## 9.4. Pharmacodynamic Analyses

Pharmacodynamics analyses will be described in the Statistical Analysis Plan.

#### 9.5. Safety Analyses

Safety analyses will be conducted using the Safety Population and summarized by treatment group as treated. The treatment-emergent period will be defined as the period of time from the first dose date and time of the randomized study drug treatment through 30 days after the last dose of study drug, or the date of initiation of another investigational agent or hormonal therapy affecting the hypothalamic-pituitary-gonadal axis or surgical intervention for endometriosis, or the date and time of the first dose of open-label extension (MVT-601-3103) study drug, whichever occurs first. Safety will be assessed through summaries of adverse events, the frequency of treatment discontinuations due to adverse events, laboratory evaluations, and bone densitometry results.

The severity of all adverse events is to be evaluated by the investigator based on the National Cancer Institute CTCAE. All adverse events will be coded to preferred term and system organ class using MedDRA 20.0 or higher. The incidence of adverse events will be presented by MedDRA system organ class and preferred term, relationship to study drug treatment, and severity. A patient reporting the same adverse event more than once is counted once, and at the maximum severity or strongest relationship to study drug treatment when calculating incidence.

Laboratory data consist of chemistry, hematology, and hormonal tests. Only data collected by the central laboratory will be used to do the analyses. The National Cancer Institute CTCAE, will be used to categorize toxicity grade for the laboratory parameters. Shift tables will be provided for each gradable parameter to summarize baseline toxicity grade versus post-baseline toxicity grade. For laboratory parameters that are not gradable by the CTCAE, a shift table based upon the normal range (low, normal, and high) will be provided for each parameter to summarize the Baseline versus post-baseline results. All data will be listed and summarized by visit. The change from Baseline to each post-baseline study visit will be presented by treatment group for each laboratory test.

For vital signs parameters, including temperature, all data will be listed and summarized by visit. The change from Baseline to each post-baseline study visit will be presented by treatment group for each parameter.

ECGs will also be read centrally. The distributions of QTc interval will be summarized at each visit. All data will be listed and summarized by visit. The change from Baseline to each post-baseline study visit will be presented by treatment group for each ECG parameter.

Bone mineral density will be determined by the central radiology laboratory at the femoral neck, lumbar spine (L1-L4), and total hip. Values at Baseline, Week 12, and Week 24 visits will be summarized by treatment group along with the absolute and percent changes from Baseline and associated 95% confidence intervals. The number and percentage of patients meeting a bone mineral density decline of at least 7% by body area (lumbar, total hip, and femoral neck) will be presented with 95% confidence intervals by treatment group.

To support the inclusion of add-back therapy in the treatment regimen, the safety endpoint of mean percent change from Baseline in bone mineral density lumbar spine at Week 12 will be analyzed using pooled data from the two replicate studies (MVT-601-3101 and MVT-601-3102) with a formal comparison of Group A versus Group B (see details in the joint Statistical Analysis Plan).

The incidence of vasomotor symptoms as assessed through adverse event reporting will be summarized by treatment arm.

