#### Safety Objectives

- To determine the safety of 24 weeks of relugolix 40 mg once daily co-administered with either 12 or 24 weeks of low-dose estradiol and norethindrone acetate;
- To determine the percent change from Baseline to Week 12 in bone mineral density at the lumbar spine (L1-L4) in Group A compared with Group B;
- To determine the change in bone mineral density after 24 weeks of treatment with relugolix 40 mg once daily co-administered with either 12 or 24 weeks of low-dose estradiol and norethindrone acetate;
- To determine the incidence of vasomotor symptoms with relugolix 40 mg once daily co-administered with either 12 or 24 weeks of low-dose estradiol and norethindrone acetate.

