# **4.2.** Discussion of Study Design, Including Dosing Rationale and Choice of Control Group

This phase 3 study is one of two replicate studies designed to establish the efficacy and safety of relugolix 40 mg once daily in women with endometriosis-associated pain. This study will focus on the primary objective of demonstrating a reduction in dysmenorrhea and NMPP, the two most common symptoms that lead to diagnosis of endometriosis. The study is designed to demonstrate the benefit and safety of relugolix 40 mg once daily co-administered with low-dose estradiol (1.0 mg) and norethindrone acetate (0.5 mg) for 24 weeks. An additional relugolix arm dosed with 12 weeks of relugolix monotherapy 40 mg once daily followed by 12 weeks of relugolix 40 mg once daily co-administered with low-dose estradiol and norethindrone acetate will be used to provide an assessment of the requirement for the low-dose hormonal add-back therapy to mitigate the adverse effects of relugolix monotherapy on bone mineral density loss and vasomotor symptoms. An open-label extension study (MVT-601-3103) is planned to provide additional safety and efficacy data through a total of up to 52 weeks.

This study is randomized, double-blind, and placebo-controlled. Patients who meet the threshold levels of NRS worst pain scores for dysmenorrhea and NMPP during a single-blind placebo Run-In Period will receive double-blind treatment for 24 weeks. The purpose of the single-blind Run-In Period is to decrease from the randomized study population who exhibit a robust placebo response or sufficient placebo response that they do not meet the minimum threshold for pain severity. Rescue analgesic medications are specified by the protocol and no other analgesics will be allowed. Starting with the second day of the Screening visit, patients will take study-specified rescue analgesic medications as needed (but not prophylactically). Patients will report their pain scores and analgesic medication usage daily in an eDiary on instruments that have undergone validation and cognitive debriefing in women with endometriosis. Appropriately selected secondary endpoints aimed at evaluation of functional effects of endometriosis, dyspareunia, and quality of life related to endometriosis-associated pain are designed to further describe the clinical benefit of treatment.

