### The study has three groups:

• Group A: relugolix 40 mg orally once daily co-administered with over-encapsulated estradiol (1.0 mg) and norethindrone acetate (0.5 mg) once daily, referred to as estradiol/norethindrone acetate for 24 weeks;

- Group B: relugolix 40 mg orally once daily for 12 weeks, followed by relugolix 40 mg orally once daily for another 12 weeks co-administered with estradiol/norethindrone acetate; and
- Group C: relugolix placebo tablet and an estradiol/norethindrone acetate placebo capsule once daily for 24 weeks.

The dose of relugolix was selected for the study (40 mg once daily) to maximally suppress estradiol levels in women with endometriosis-associated pain so that all women start from a stable floor of very low estrogen. Estradiol/norethindrone acetate will be co-administered to add-back, in a controlled fashion, a dose of estradiol known to prevent bone mineral density loss in the majority of women and to mitigate other tolerability adverse effects such as vasomotor symptoms. To ensure blinding, an over-encapsulated fixed-dose combination tablet of estradiol/norethindrone acetate will be co-administered with relugolix once daily.

Treatment Group A has been selected to provide the maximal benefit/risk ratio to women by providing relugolix 40 mg once daily, the dose known to maximally suppress estradiol levels and to provide the greatest decrease in endometriosis-associated pain, co-administered with low-dose estradiol/norethindrone acetate add-back therapy, to protect against bone mineral density loss and improve tolerability. Treatment Group B is intended to assess the requirement for low-dose hormonal add-back therapy to mitigate the adverse effects of relugolix monotherapy on bone mineral density loss and vasomotor symptoms. Placebo has been selected as the comparator because it facilitates double-blinding and allows for a clearer characterization of the safety and efficacy profile of relugolix, a new chemical entity, than would be possible with an active comparator. Furthermore, there is no single standard-of-care treatment for endometriosis-associated pain.

The selection of the proposed active treatment arm is supported by the following evidence-based reasons:

- Relugolix 40 mg once daily suppressed serum estradiol to less than postmenopausal levels, and significantly reduced endometriosis-associated pain in a well-designed large dose-finding phase 2 study.

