# **5.3.** Randomization and Stratification

At the Baseline Day 1 visit, patients will be randomized in a 1:1:1 ratio to 1 of 3 treatment groups, as described in Table 5-3.

Table 5-3 Protocol MVT-601-3102 Treatment Group Randomization

Treatment Group	Randomized Treatment	Approximate Number of Patients
Group A	Relugolix 40 mg tablet co-administered with 1.0 mg estradiol / 0.5 mg norethindrone acetate capsule for 24 weeks	200
Group B	Relugolix 40 mg tablet co-administered with estradiol/norethindrone acetate placebo capsule for 12 weeks followed by relugolix 40 mg tablet co-administered with 1.0 mg estradiol / 0.5 mg norethindrone acetate capsule for 12 weeks	200
Group C	Relugolix placebo tablet co-administered with estradiol/norethindrone acetate placebo capsule for 24 weeks	200

Randomization will be stratified by geographic region and duration of endometriosis as follows:

- Geographic region: North America versus Rest of World; and
- Years since surgical endometriosis diagnosis: < 5 or  $\ge 5$  years.

Patients are assigned to 1 of the 3 treatment groups in accordance with the randomization schedule (see additional information on randomization in Section 4.5).

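### Does a whole-period summary of vasomotor symptoms blunt the comparison of Groups A and B on add-back therapy?

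*Protocol*

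**What the plan says.** On vasomotor symptoms, Protocol Section 9.5 has one sentence: "The incidence of vasomotor symptoms as assessed through adverse event reporting will be summarized by treatment arm". The same section defines one treatment-emergent period. It runs from the first randomized dose to 30 days after the last dose, or to an earlier event; the list of such events ends with "or the date and time of the first dose of open-label extension (MVT-601-3103) study drug, whichever occurs first". On counting it says: "A patient reporting the same adverse event more than once is counted once".

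The matching safety objective in the Synopsis is: "To determine the incidence of vasomotor symptoms with relugolix 40 mg once daily co-administered with either 12 or 24 weeks of low-dose estradiol". (The add-back also contains norethindrone acetate.) The Synopsis endpoint is simply the incidence of these symptoms. Section 3 pairs the two, and no week is attached to either.

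On design, Table 5-3 in Section 5.3 gives Group B's regimen as "Relugolix 40 mg tablet co-administered with estradiol/norethindrone acetate placebo capsule for 12 weeks followed by relugolix 40 mg tablet co-administered with 1.0 mg estradiol". That second stage, which also includes norethindrone acetate, lasts 12 weeks, so from Week 12 the regimen matches Group A's. Section 4.2 explains the arm: "Treatment Group B is intended to assess the requirement for low-dose hormonal add-back therapy to mitigate the adverse effects of relugolix monotherapy", with bone loss and vasomotor symptoms both named. For bone, Section 9.5 does set a time point: "the safety endpoint of mean percent change from Baseline in bone mineral density lumbar spine at Week 12 will be analyzed", as a formal comparison of A with B on data pooled from the two replicate studies.

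Two general statements also bear on the point. Under Criteria for Evaluation, the Synopsis makes the safety comparison between the two relugolix groups descriptive. The opening of Section 9 leaves detailed methods and analyses to the SAP, which was not available for this review.

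**The concern.** Group B is in the trial to show whether the regimen needs "add-back therapy to mitigate the adverse effects of relugolix monotherapy on bone mineral density loss and vasomotor symptoms". The arms can inform that question directly only while their treatments differ, in the first 12 weeks. A cumulative incidence over the whole window adds later first onsets from a time when both arms take relugolix with add-back, plus up to 30 days off drug for women who do not enter the extension. If late onsets are about equally likely in both arms, they pull the two incidences together. The summary also does not show which Group B onsets arose on monotherapy and which on the combination.

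The contrast with bone density makes this look like an oversight: one half of Group B's purpose gets a Week 12 comparison and the other half does not. The descriptive evidence that add-back reduces vasomotor symptoms would be at stake. No hypothesis test, error rate or sample size depends on it.

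**Working it through.** The protocol gives no vasomotor rate, so there is no stated figure to reproduce. The check has three parts.

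**1. Analysis against objective.** The objective asks for incidence under relugolix with either 12 or 24 weeks of add-back, that is, under each whole regimen. A by-arm summary over the whole treatment-emergent period answers that. The sentence in Section 9.5 does not say that it will be the only vasomotor table, and nothing excludes a split at Week 12.

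**2. Time on different regimens.** In Table 1-1 the Week 12 visit is Day 85 and the Week 24 visit is Day 169, with the last dose the day before. That gives 84 days before the switch and 168 days on drug.
- Women entering the extension: 84/168 = 50%.
- Women completing 24 weeks and not entering: 84/(168 + 30) = 84/198 = 42%.
- A woman whose last dose is on Day 84: 84/(84 + 30) = 84/114 = 74%.
- A woman who stops after 56 days: 56/(56 + 30) = 56/86 = 65%.

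These are shares of calendar time. They do not measure dilution, because each woman is counted once, at her first event. What matters is how many first onsets come after Week 12.

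**3. Effect on the difference.** Let a and b be the Week 12 incidences in A and B, and hA and hB the risks of a first onset later among women still event-free. Then:
- Whole-window incidence: A = a + (1 − a)hA and B = b + (1 − b)hB.
- Difference: (b − a) + (1 − b)hB − (1 − a)hA, which is (b − a)(1 − h) when hA = hB = h.
- 95% half-width: 1.96 × √[A(1 − A)/200 + B(1 − B)/200], with 200 per arm from Table 5-3.

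All rates below are assumptions. With a = 10% and b = 35%:

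| Later risk h, both arms | A | B | Difference (points) | Half-width (points) |
|---|---|---|---|---|
| 0 (same as Week 12 cut) | 10.0% | 35.0% | 25.0 | 7.8 |
| 3% | 12.7% | 36.95% | 24.25 | 8.1 |
| 5% | 14.5% | 38.25% | 23.75 | 8.3 |
| 10% | 19.0% | 41.5% | 22.5 | 8.7 |
| 20% | 28.0% | 48.0% | 20.0 | 9.3 |

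With a = 5% and b = 20%, the difference of 15.0 becomes 14.55 (h = 3%) or 13.5 (h = 10%).

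With unequal later risk, starting again from 10% and 35%:
- hA = 5%, hB = 2%: 36.3% − 14.5% = 21.8 points.
- hA = 5%, hB = 8%: 40.2% − 14.5% = 25.7 points.
- No change when hB/hA = (1 − a)/(1 − b) = 0.90/0.65 = 1.38.

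So the direction is not fixed. The protocol's background suggests that h is small: Section 2.2.2 has estradiol falling within days, and Section 2.2.4.1 reports a clear hot-flush contrast in a 6-week study. If onset is that early, the whole-window and Week 12 incidences nearly coincide.

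**The case for a change.** The strongest case for the concern is that the protocol, not the SAP, states the window, the counting rule and the by-arm summary, names vasomotor symptoms as part of Group B's purpose, and fixes Week 12 for bone. Relative measures also suffer more than the difference does. With 10% and 35% at Week 12 and h = 10%, the risk ratio falls from 35.0/10.0 = 3.50 to 41.5/19.0 = 2.18, and the difference divided by its standard error falls from 6.27 to 5.05. Even where late onset leaves the difference intact, Group B's monotherapy onsets are not shown apart from its later ones.

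This much stands: a Week 12 split would be a sharper descriptive look at add-back, and the whole-window figure is not a same-period contrast of add-back with none. It does not make the stated analysis wrong.

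The bone parallel is weaker than it looks. The bone comparison is formal and pooled over two studies, so its time point has to be set in advance. Bone density is also a state measured at a visit, and a Week 24 value no longer reflects monotherapy alone. Vasomotor incidence counts whether a woman ever reported the event, so an onset on monotherapy remains in Group B's count whatever happens after the switch. Adverse event start dates are among the source data required by Section 10.1.5, so a Week 12 table can be made without any change to the protocol or to data collection.

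**Conclusion.** The concern does not hold. The by-arm summary answers the vasomotor objective and endpoint as written, contradicts nothing in the protocol, and still gives a sound descriptive contrast of A with B. A Week 12 cut of a descriptive adverse-event table is a reasonable extra, of a kind commonly settled in the SAP, and the protocol leaves room for it.

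The possible loss is small and uncertain in direction. For assumed incidences of 10% and 35% it is 0.75 to 2.5 points at equal later risks of 3% to 10%, against a half-width of about 8 to 9 points. At h = 20% it would be 5.0 points, and it disappears or reverses once Group B's later risk reaches or exceeds 1.38 times Group A's. These sizes rest on assumed rates, on 200 women per arm, and on applying Section 9.5's general window and counting rule to the vasomotor summary. The judgement that nothing is wrong does not depend on the assumed rates.
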